5. Package containing blinded study drug supply, study journals (medicine log, symptom tracker and experience log) and study documents (details on aims, design, consent forms, and any additional instructions) are delivered to the address provided by participant as place of residence during study. Delivery of blind study drug supply will occur in two shipments, each containing a 30-day supply. Day 1 is defined as the first day the blinded study drug is taken by the participant.
6. Each day active medication is taken (HCQ or placebo), participants will record 1) temperature (to be reported twice daily, either via thermometer or self-report); 2) time medication taken; and 3) any symptoms and AEs.
7. Every week, clinical research coordinators will review the study portal to assess for AEs and indication of reported symptoms indicative of influenza like illness. The research coordinator will also review self-reported fever and/or temperature. If COVID-19 symptoms are evident, the research coordinator will outreach to the HCW (at clinic or by phone). Clinical research coordinators may clinically escalate any medical determinations to Co-PI following study portal review.
8. The HCW also has access to the study coordinators via the study phone number. If the HCW feels symptomatic, then he/she should call the clinical research coordinator team, and document symptoms in the study portal. Clinical research coordinators may clinically escalate any medical determinations to Co-PI.
9. If during the study symptoms indicative of an influenza like illness present, participant will be asked to comply with their employer's potential or confirmed COVID-19 incident protocol and be tested for COVID-19 by an accepted method. Participants negative for COVID-19 continue with the assigned blinded study drug regimen.
10. If confirmed COVID-19 diagnosis, participant will be unblinded. Participants assigned to HCQ can continue with medication schedule. Individuals assigned to the placebo arm will be offered the opportunity to cross-over to HCQ 600 mg daily for 14 days. Individuals will be expected to continue self-reporting temperature, time medication taken and any symptoms/AEs into the study portal while taking active HCQ medication.
11. Participants who remain undiagnosed for COVID-19 by the end of the medication period (Day 60) will be asked to undergo COVID-19 and serology testing for IgM/IgG on either Day 61, 62, or 63.

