COVID-19/SARS-CoV-2 testing: Upon the presentation of symptoms indicative of an influenza like illness, participants will be asked to undergo testing for SARS-CoV-2 virus. Participants undiagnosed for COVID-19 at Day 60 will also be tested for SARS-CoV-2 and IgM/IgG antibodies (via serology testing) on either Day 61, 62, or 63.

Clinical Symptom monitoring: The study team will assess AEs, symptoms, and record temperature (either reported temperature or self-report of fever) for any participants taking active medication (placebo or HCQ). Worsening COVID symptoms and/or new or worsening AE's will be reviewed by the PI's for causality to study drug. The rate of conversion to receiving a positive COVID-19 test result in each arm at the 2-month mark will be used to assess the primary endpoint.

Pill count and Journal: Participants will be contacted to compare data entry on the portal and collect any missed entries over the phone.

Participants will be instructed to call 911 upon immediate presentation of the following symptoms as identified by the CDC as requiring emergency action: bluish lips or face; new confusion/dizziness or inability to arouse; persistent pain or pressure in the chest (not caused by coughing); and difficulty breathing (including severe shortness of breath and single word speech).

Participant confidentiality is strictly held in trust by all personnel granted access to the trial data. Therefore, the study data, and all other information generated will be held in strict confidence. No information concerning the study, or the data will be released to unauthorized parties.

The study investigators and study team, the research sponsor and its designees, personnel from ProHealth with authorized access to study data, government agencies, reviewing Institutional Review Board (IRB), regulatory agencies and/or company supplying study product may inspect all documents and records required to be maintained by the sponsor, including but not limited to, clinical, pharmacy and lab records for participants enrolled in the study. All applicable parties will permit access to such records.

The participant's study contact information will be securely stored within the online study portal for internal use during the study. At the end of the study, all records will continue to be kept in a secure location for as long as dictated by the reviewing IRB and institutional policies.

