8.5 Hydroxychloroquine Dose Reduction

Any Adverse Event Grade 3 or higher requires HCQ to be withheld. Treatment may be resumed once toxicity is \leq Grade 2 according to the below Dose Reduction Schema (Table 1). If toxicity does not resolve or improve to \leq Grade 2 within 7 days, participant will be withdrawn from active treatment unless granted an exception by the Medical Monitor. Medical Monitor should be notified of all toxicities requiring dose withholding or dose adjustments via email or phone.

Any AE = Grade 2 and **attributed as possibly, probably or definitely related to HCQ** will result in a dose reduction of HCQ as described in Table 1.

If AE remains = Grade 2 following the first dose reduction **and attributed as possibly, probably or definitely related to HCQ** following the second dose reduction, then the participant should discontinue treatment.

No more than 2 dose reductions are allowed. It is recommended that dose reductions occur at a minimum of 48 hours apart.

Table 1: Dose Reduction Schema

Sub-Study	Dose mg/day	First dose reduction	Second Dose reduction
1 (PATCH 2)	400 mg (two tablets) twice daily	400mg (two tablets) once daily	200 mg (one tablet) once daily
2 (PATCH 3)	600 (three tablets) mg daily	400 mg (two tablets) once daily	200 mg (one tablet) once daily

Reported non-serious toxicities attributable to HCQ include nausea, anorexia, vomiting, constipation, diarrhea and rash. For any of these AEs occurring at Grade < 2 , HCQ may be continued and the AE managed with supportive care. For **Any AE** with a Grade ≥ 3 , HCQ will be held until the toxicity improves to \leq Grade 2, after which HCQ may be restarted at a reduced dose as described in Table 1.

Example: Management of diarrhea in randomized subjects

Grade 1: (an increase in stool up to 3 per day) results in no change to HCQ

Grade 2: (an increase in stool up to 4-6 per day) results in a Dose Reduction according to Table 1

Grade 3+: (an increase in stool up to 7 or more per day) results in Withholding of HCQ until AE at Grade level 2 or less, followed by a reduction in dose per Table 1.

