PATCH 3 (Sub-Study 2), Prophylaxis in Health Care Workers: The transmission of SARS-COV-2 from patient to hospital worker depends on many factors including specifics of standard care to prevent transmission, but especially on the number of patients seen at a given hospital or outpatient practice. Across China the reported hospital worker infection rate is 3.8%, but in Wuhan it is reported as 58% at the height of the epidemic. We will use a 10% transmission rate as the null hypothesis (low dose group). In order for HCQ to be considered effective our alternative hypothesis will be a 1% transmission rate. With a 1:1 randomization for the HCQ to control arms we would require a total of 350 health care workers across all participating ProHealth NY and AHN sites. With the placebo group of 175 participants and the high dose HCQ arm of 175 participants, a one-sided z-test ($\alpha=0.05$) comparing the rates in the two groups would have an at least 80% power to detect a significant difference when the difference in the population rates is at least 9%.

The *hypothesis* will be tested using a one-sided test, with a z-score corresponds to the log of the odds-ratio for the rate of transmission between the two groups. We will obtain the estimate of the odds ratio, and 95% CI, from logistic regression.

Interim analysis: We will perform two interim analyses at 25% and 50% completion, testing for early efficacy or futility, using z-score boundaries that follow Hwang-Shih-DeCani alpha spending rules. Following those rules, we have 80% power using 100% of the sample, if our 10% versus 1% scenario is true.

Z-Value Boundaries

Stage	Boundaries		Information Proportion
	Efficacy	Futility	
1	2.9473	-1.2318	0.2500
2	2.5825	-0.2676	0.5000
3	1.6664	1.6664	1.0000

P-Value Boundaries

Stage	Boundaries		Information Proportion
	Efficacy	Futility	
1	0.00160	0.89099	0.2500
2	0.00491	0.60550	0.5000
3	0.04782	0.04782	1.0000

16.2 Analysis of Secondary Endpoints.

Secondary outcomes will be analyzed as summary statistics, with group means, odds-ratios, and 95% CIs. We may conduct exploratory analyses using regression methods appropriate for each type of measure. Tests for significance of estimated parameters will not be reported as we will not be controlling for multiple testing.

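### PATCH 3 ties scheduled symptom recording to taking study drug, so undiagnosed participants who hold or stop drug leave the weekly screen; if that happens more on HCQ, missed infections favour HCQ

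*Combined protocol and SAP*

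**What the plan says.** Section 4.0, PATCH 3 item 6, sets the recording rule: "Each day active medication is taken (HCQ or placebo), participants will record 1) temperature", together with dosing time, symptoms and adverse events. Item 7 has coordinators review the portal weekly and contact the participant if COVID-19 symptoms are evident. Section 8.4 (PATCH 3, clinical symptom monitoring) has the study team assess symptoms and temperature "for any participants taking active medication (placebo or HCQ").

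Other text points the other way or supplies a backstop:

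- The PATCH 3 FAQ in Appendix 4 asks participants to upload temperature and adverse events daily throughout the study.
- Item 8 tells a worker who feels ill to call.
- Item 9 calls for testing when an influenza-like illness appears during the study, with no on-drug condition.
- Item 11 asks everyone still undiagnosed at Day 60 to have virus and IgM/IgG tests on Day 61, 62 or 63.
- Section 8.4 (pill count and journal) provides phone contact to collect missed entries, with no stated frequency.

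Time off drug is expected. Section 8.5 says "Any Adverse Event Grade 3 or higher requires HCQ to be withheld", and provides for reduction and then discontinuation for related Grade 2 events. Section 12.0 lists refusal of treatment and toxicity delays longer than 7 days among the reasons for withdrawal.

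PATCH 2 differs. Its item 8 asks for entries every day without reference to drug intake, and item 9 adds three calls a week.

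**The concern.** The point concerns participants not yet diagnosed. The weekly review can act only on what has been entered. Under item 6, a day off drug calls for no entry, so it is not a missed entry either. A worker on hold or off drug therefore loses the one scheduled prompt that leads to outreach and testing.

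That worker can still count in the primary analysis. Section 15.1 makes participants evaluable after one continuous week of HCQ, so an HCQ participant who stops at Day 10 qualifies, and an infection not found later is counted as no infection.

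If the loss were equal in the two arms it would not bias the test under the null. It may not be equal. The Appendix 4 side-effect guide lists nausea, stomach pain and stomach cramps in 10% or more of people receiving HCQ. That is a side-effect frequency, not a stopping rate, but it makes more holds and stops on HCQ plausible. Any excess of missed infections on HCQ would lower its recorded infection rate and push a one-sided test towards a claim of prevention.

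**Working it through.** **1. The plan's own figures.** Section 16.1 states "We will use a 10% transmission rate as the null hypothesis" and "our alternative hypothesis will be a 1% transmission rate", with 175 per arm, one-sided alpha 0.05 and at least 80% power. With these inputs the power is 98.2% for a difference in proportions and 91.2% for a Wald test on the log odds ratio. The stated 80% is therefore true as a lower bound. The PATCH 3 efficacy boundaries (2.9473, 2.5825, 1.6664) give an overall one-sided error of 0.0500. The final boundary alone gives P(Z > 1.6664) = 4.8%, which is the no-bias reference below.

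**2. Inputs for the bias check.** From the plan: 10% infection (here in both arms, so no drug effect), 60 days, 175 per arm, final boundary 1.6664. Assumed, because the documents give no such figures: infections spread evenly over 60 days, the share of each arm that stops, the stopping day, and the share of off-drug infections never found.

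**3. Formulas.**

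- Recorded rate = 0.10 × (1 − share stopping × (60 − stopping day)/60 × share missed), by arm.
- Shift = log odds ratio of the recorded rates ÷ its standard error, where SE = √[1/(175·p·(1−p)) summed over arms].
- Error = P(Z > 1.6664 − shift). This treats the final look only.

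**4. One case in full** (25% of HCQ and 5% of placebo stop at Day 15; 75% missed).

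- HCQ: 0.10 × (1 − 0.25 × 45/60 × 0.75) = 0.0859.
- Placebo: 0.10 × (1 − 0.05 × 45/60 × 0.75) = 0.0972.
- Log odds ratio 0.135, SE 0.371, shift 0.36; P(Z > 1.30) ≈ 9.7%.

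**5. Range.**

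| Stop, HCQ / placebo | Stopping day | Missed | Recorded, HCQ / placebo | One-sided error |
|---|---|---|---|---|
| none, or equal in both arms | any | any | equal | 4.8% |
| 10% / 5% | 15 | 25% | 9.81% / 9.91% | 5.1% |
| 10% / 5% | 15 | 50% | 9.63% / 9.81% | 5.4% |
| 15% / 5% | 30 | 50% | 9.63% / 9.88% | 5.6% |
| 15% / 5% | 15 | 50% | 9.44% / 9.81% | 6.1% |
| 25% / 5% | 15 | 75% | 8.59% / 9.72% | 9.7% |
| 30% / 10% | 10 | 100% | 7.50% / 9.17% | 13.5% |

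**6. Cross-check by another route.** Exact enumeration of the pooled z-test at the unadjusted 5% critical value has a no-bias error of 5.1%. With 5% of placebo participants off drug for half of follow-up and 25-100% of off-drug infections missed, the error is 5.3-6.0% if 10% of HCQ participants are off drug, 5.7-8.1% if 20%, and 6.2-10.9% if 30%. With 20% off drug in both arms and half missed, it stays at 5.1%. Power at 10% versus 1% remains about 99% in all the unequal cases, so the exposure is a false positive, not lost power.

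**The case against.** The strongest reply is that several detection routes do not depend on drug intake. Item 9 testing applies throughout the study, and agreement to it is an inclusion criterion. These are health care workers under employer COVID-19 protocols who are told to call when ill. The missed-entry calls are staff-initiated. The Day 61-63 visit includes IgM/IgG as well as a virus test, and antibodies are what could reveal an infection weeks earlier. A reader might infer from item 6 that endpoint detection ends when drug stops, or that only a swab remains at the end. The documents support neither reading.

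The stopping premise is also soft. Under 8.5, common low-grade symptoms do not lead to a hold. Section 2.3 reports grade 3-4 non-hematological toxicity below 10% in cancer patients, most of them escalated to 1200 mg per day. The FAQ suggests that daily recording was intended for everyone, and the PATCH 3 process-flow figures, which are not visible in the text reviewed, may address off-drug reporting.

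Much of this stands, and it limits the likely size. It does not close the gap:

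- Item 9 testing needs someone to notice and report symptoms, and the scheduled prompt for that is what lapses.
- Section 15.2 defines infection by measurement of SARS-CoV-2 and does not say whether serology alone counts. With no baseline test, a positive antibody result cannot date the infection.
- Section 12.0 does not say that withdrawn participants still have the Day 61-63 tests, so this backstop is least certain for the people at issue.
- The FAQ contradicts item 6 rather than overriding it.

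**Conclusion.** The point holds as a gap in scheduled detection and an inconsistency to reconcile. As item 6 and 8.4 are written, undiagnosed PATCH 3 participants who hold or stop drug have no scheduled symptom entries for the weekly review, while the FAQ says otherwise. If stopping is commoner on HCQ, the resulting misses favour HCQ.

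The size cannot be derived from the documents. Under assumed rates, the one-sided error is about 5-6% in mild cases against 4.8% with no bias. It reaches about 10-13.5% only when a quarter or more of the HCQ arm stops early, far fewer stop on placebo, and off-drug infections are mostly or wholly missed. The top figure requires every backstop, including Day 61-63 testing, to find nothing. A reader might take 10-13.5% as the expected error; the documents do not support that. Nor is there inflation without an imbalance between arms.

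The change is still worth making: it costs little, and infections never detected cannot be recovered in analysis.

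**What to change.** 1. Section 4.0, PATCH 3 item 6: require recording every day from Day 1 to Day 60, or until COVID-19 diagnosis, whether or not study drug is taken.
2. Section 8.4, PATCH 3 clinical symptom monitoring: delete the on-drug condition.
3. Align both with the Appendix 4 FAQ and the participant journal.
4. Section 12.0: state that participants who stop drug but consent to follow-up keep symptom recording, symptom-triggered testing and Day 61-63 testing. Without this, rewording item 6 may not reach long-term stoppers.

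It would also help to say in section 15.2 whether a positive serology alone counts for the primary endpoint.

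The cost is protocol and journal wording and a few more portal entries from participants off drug, with no added visits. No dose, hold or discontinuation rule changes.

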9. Three times a week, participants will be called by clinical research coordinators to assess AEs and symptoms with all discussions well-documented. Clinical research coordinators may clinically escalate any medical determinations to Co-PI
10. After Day 14, which marks the end of the treatment period, participants will no longer be expected to continue self-reporting information into the study portal. Participant will undergo follow-up testing for COVID-19 at two additional time points. The first will be either day 15, 16 or 17, with the second on either on day 29, 30 or 31
11. If during active participation, the participant reports worsening of symptoms related to COVID-19 from baseline, this is reported to the PI for further clinical evaluation

Participant Procedure PATCH 3 (Sub-Study 2) (See study process flows)

1. Interested participants self-refer for study by completing online eligibility checklist on study portal (www.patchstudy.com)
2. Review inclusion and exclusion criteria:
 - Currently employed as a health care worker ([name]; Doctor of Osteopathic Medicine, DO; Nurse Practitioner, NP; Physician's Assistant, PA; and [name] or other members of the medical care team with significant COVID-19 exposure);
 - Asymptomatic and presumed negative for COVID-19 (no confirmatory testing conducted);
 - Scheduled for an average of >20 hours per week of clinical care over the next two months (or equivalent indicating at least part-time employment).
 - Willing to comply with their employer's potential or confirmed COVID-19 incident protocol
 - Agrees to undergo COVID-19 testing per standard of care using an FDA approved method upon the presentation of symptoms indicative of an influenza like illness (if a confirmatory COVID-19 diagnosis is given, participant will be offered to cross-over to HCQ 600 mg qd for 14 days.)
3. Reviews the study and the Informed Consent Form with the subject and obtains informed consent via DocuSign
4. Participant study ID is assigned, and subsequently, randomized into a study arm (HCQ or placebo).

PATCH 2 & 3 TRIAL

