8.4 Participant Safety Monitoring and Data Collection

Adverse events will be captured via self-report by participants within the study portal. Participants are instructed to contact the study team at the phone number provided in the Welcome Packet to report all adverse events. The study team will reach out to the participant to gather additional information surrounding the adverse event in order to complete DAIDS grading if necessary. Additional information pertaining to the adverse event will be captured within the study portal by the study team and reviewed by the PI's for causality to study drug. Adverse events meeting seriousness criteria will be reported to the IRB as noted below.

PATCH 2 (Sub-Study 1):

Clinical Symptom Monitoring: Participants will be contacted three times per week to assess AEs and COVID-19 symptoms and collect/review self-reported AE's. Worsening COVID symptoms and/or new or worsening AE's will be reviewed by the PI's for causality to study drug.

Temperature Measurements: Home quarantined participants will be asked to report twice daily either presence of fever or temperature and record the measurements.

COVID-19/SARS-CoV-2 Testing: On Days 15-17 and 29-31, participants will undergo follow-up testing for COVID-19.

Pill Count and Journal: Participants will be contacted three times per week and following the end of treatment to compare data entry on the portal and collect any missed entries over the phone.

Monitoring Co-Inhabitants: Participants will be contacted three times per week to identify if any co-inhabitants have developed symptoms and/or tested positive for COVID-19. Participants will also be asked to provide a description of co-inhabitants' symptomology, and time of positive testing for COVID-19 via self-reporting.

PATCH 3 (Sub-Study 2):

Adverse events will be captured solely based on participant self-reporting via the study portal and/or by calling the study team at the number provided in the Welcome Packet. The study team will review the portal for self-reported AE's not previously reported to the study team. New AEs not previously reviewed which cannot be

PATCH 2 & 3 TRIAL

graded based upon self-reported data within the portal will require follow-up from the study team to gather additional information from the participant. New or worsening AE's will be reviewed by the PI's for causality to study drug.

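### PATCH 3: an adverse event entered only in the portal can wait up to a week for staff review, although Section 8.5 requires a hold at Grade 3 or higher

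*Combined protocol and SAP*

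**What the plan says.** **What triggers action.** Section 8.5 states "Any Adverse Event Grade 3 or higher requires HCQ to be withheld". It also calls for a dose reduction when a Grade 2 event is at least possibly related to HCQ. An event that has not improved to Grade 2 or below within 7 days leads to withdrawal from active treatment, unless the Medical Monitor grants an exception.

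**How PATCH 3 events reach staff.** Section 8.4 says: "Adverse events will be captured solely based on participant self-reporting via the study portal and/or by calling the study team". Participants make daily entries (Section 4.0, PATCH 3 procedure, item 6: "Each day active medication is taken (HCQ or placebo), participants will record" temperature, dosing time, symptoms and AEs). Staff look at those entries on a weekly schedule (item 7: "Every week, clinical research coordinators will review the study portal to assess for AEs"). Item 7 attaches outreach to one finding only: "If COVID-19 symptoms are evident, the research coordinator will outreach to the HCW". Section 8.4 adds that staff check the portal for AEs that have not already reached them, and follow up when an entry cannot be graded as it stands. It gives no frequency for that check.

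**The phone route.** The general part of Section 8.4, which covers both sub-studies, instructs participants to phone in all AEs. Item 8 adds: "If the HCW feels symptomatic, then he/she should call the clinical research coordinator team". The side-effect guide in the PATCH 3 job aid (Appendix 4) tells participants to inform staff of side effects without delay.

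**PATCH 2 for comparison.** Section 4.0, PATCH 2 procedure, item 9: "Three times a week, participants will be called by clinical research coordinators to assess AEs and symptoms".

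**The concern.** A hold or reduction under Section 8.5 needs someone on the study team to know of the event, grade it and, for Grade 2, obtain a causality judgement. The visible text does not tell participants to stop dosing on their own at a given severity, and the PATCH 3 bottle label gives a plain daily instruction. If an event sits in the portal unseen, the participant has no stated reason to stop, and dosing continues after an event for which the protocol says drug must be withheld.

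Two things are at stake. One is safety in the sub-study with the longer course (up to 60 days, against 14 in PATCH 2), in a trial that requires no safety laboratory tests (Section 9.5). The other is the dosing record: doses taken between the event and its review do not follow the Section 8.5 schema, and this would be adherence to the reporting process as written, not a deviation from it.

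**Working it through.** There is no sample-size, power or alpha figure to reproduce. The check sets the stated intervals side by side.

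**Inputs**
- Scheduled PATCH 3 portal review: every 7 days (Section 4.0, PATCH 3 procedure, item 7).
- Participant entry: daily (item 6).
- Permitted reporting routes: portal, phone, or both (Section 8.4, PATCH 3).
- Dosing: three 200 mg tablets once a day (Section 6.0).
- PATCH 2 staff calls: three a week (Section 4.0, PATCH 2 procedure, item 9).

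**Wait for a portal-only entry**
1. Shortest wait: 0 days (entered just before a review). Longest: 7 days (entered just after one).
2. Mean wait, assuming entries are uniform over the week: 7 / 2 = 3.5 days.
3. Scheduled doses in the longest wait: 7 days × 1 dose a day = 7 doses, that is 7 × 3 = 21 tablets, or in the HCQ arm 21 × 200 mg = 4,200 mg. This assumes the participant takes every dose.
4. The wait is counted from portal entry. Any lag between onset and entry, or any follow-up needed to grade the entry, comes on top.

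**Wait for an event phoned in at once:** none from this source.

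**PATCH 2 comparison:** 7 / 3 = 2.3 days between calls if evenly spaced, or at most 3 days on a 2-2-3 day pattern (an assumption; the spacing is not stated).

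**When the 7-day limit starts.** Sections 8.2 and 8.5 place the limit directly after the delay or hold but do not name its first day. Section 12 lists a treatment delay of more than 7 days due to toxicity as a reason for withdrawal, which counts days of delay and so suggests the hold. Take an event entered on the day of onset, in the longest-wait case:
- Counted from onset, the 7 days end at about the first review.
- Counted from the hold, they end about 7 + 7 = 14 days after onset.

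The two readings differ by as much as the review interval itself, so the start needs to be stated.

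**The case against.** The strongest reply is that prompt reporting is already instructed three times: phone in all AEs (Section 8.4), call if symptomatic (item 8) and tell staff without delay (Appendix 4). On this view the weekly review is only a backstop, and the wait arises only if a health care worker with a serious event uses the portal and does not call. This stands as a limit on the size of the problem. It does not close the gap. Each of those routes depends on the participant, Section 8.4 accepts a portal entry alone, and the same section expects to find portal events that staff have not heard about. Other PATCH 3 contact, such as the pill-count check in Section 8.4, has no stated frequency.

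A second reply is that the process flows, to which Section 14 defers the schedule of events, may contain an alert. The PATCH 3 AE flow figure is not shown, so this cannot be excluded. A third is that PATCH 2 enrols febrile patients aged 50 to 75 and PATCH 3 enrols asymptomatic workers, so different contact intensity is defensible. That is fair, and the point does not rest on the contrast.

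A reader might infer three stronger claims that the documents do not support:
- That weekly review conflicts with the 48-hour spacing. The text reads "It is recommended that dose reductions occur at a minimum of 48 hours apart": a recommended minimum gap, not a deadline, so a longer interval cannot breach it.
- That the 7-day limit may already have expired at the first review. This needs the clock to start at onset. Section 12 points to the hold, and Sections 8.2 and 8.5 provide a Medical Monitor exception.
- That Section 8.5 is the trial's only dose-safety rule. Sections 8.2, 8.3, 9.5 and 12 also govern holding or stopping.

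**Conclusion.** The point holds in a limited form, as a cheap improvement. For PATCH 3 events entered in the portal without a call, the visible text allows 0 to 7 days, and so up to 7 scheduled daily doses, before staff can apply a hold that Section 8.5 makes mandatory. The 3.5-day mean rests on uniform entry over the week.

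The documents give no basis for estimating how many events would take this route. The planned 175 participants in the HCQ arm are all under this process, but that is not a count of people affected. The conclusion also depends on the process-flow figure that is not shown containing no faster alert. If it does contain one, what remains is to state it in the text. Separately, the start of the 7-day limit is not stated and needs reconciling.

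**What to change.** Reconcile Section 4.0 (PATCH 3 procedure, item 7), Section 8.4 and Section 8.5 as follows:
1. Have the portal alert the coordinators the same day to any PATCH 3 AE entry that may meet a Section 8.5 threshold, and say so in item 7. Keep the weekly review as a backstop. If such an alert already exists in the process flows, state it in the text.
2. Align the PATCH 3 reporting wording in Section 8.4 with the instruction in the same section to phone in all AEs, so that a portal entry alone no longer satisfies the text.
3. Have the sponsor reconcile Sections 8.2, 8.5 and 12 on when the 7-day limit starts. No start point is proposed here, and no dose, hold or reduction threshold changes.

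The cost is one notification rule and a few sentences of text. The downside is some extra coordinator calls from false alerts. No new visit or procedure is needed.
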